4.1 Study Endpoints

Primary Endpoint

Phase I:

Safety and Tolerability: The incidence, type, and severity of adverse events (AEs) assessed according to the National Cancer Institute-Common Terminology Criteria for Adverse Events (NCI-CTCAE) V5.0, physical examination findings, clinical laboratory values, vital signs and Electrocardiograms (ECGs)

The MTD, if any, and RP2D for HH2710 will be determined based on safety, tolerability, PK, preliminary efficacy, and other available data.

Phase II:

Tumor objective response rate (ORR) based on RECIST version 1.1.

Secondary Endpoints

Phase I:

Peak plasma concentration (Cmax), peak time (tmax), area under the plasma concentration-time curve from time 0 to time (t) (AUC0-t), plasma elimination half-life (t1/2), plasma clearance rate constant (λ_z), apparent clearance (CL/F), apparent volume of distribution (Vz/F).

Phase II:

the duration of response (DoR), progression-free survival (PFS), disease control rate (DCR), time to response (TTR), time to progression (TTP), and 1-year overall survival (OS) rate.

The incidence, type, and severity of adverse events (AEs) assessed according to the National Cancer Institute-Common Terminology Criteria for Adverse Events (NCI-CTCAE) V5.0, physical examination findings, clinical laboratory values, vital signs and Electrocardiograms (ECGs).

Exploratory Endpoints

Phase I:

ORR, DoR, DCR, PFS and TTR.

Changes in PD markers of HH2710 efficacy including phosphorylation of RSK (pRSK) and total RSK.

4.2 Planned Covariates

No covariates will be accounted for in Phase I (dose-finding and dose expansion). In Phase II (cohort extension), analyses will be analyzed by subgroups of tumor types and/or genetic mutations in order to evaluate the preliminary efficacy.

5. Hypotheses and/or Estimations

Phase I:

No hypothesis for this phase since the primary endpoint are safety profile, MTD and RP2D.

Phase II for Cohort 1 and Cohort 2:

In Cohort 1 and Cohort2, the null hypothesis of the response rate is 0.02, and the alternative hypothesis is 0.16. The design controls the type I error rate at 0.1 and yields the power of 0.8201 under H1.

We will perform an interim analysis for the first 23 patients. When at least 2 patients experience CR or PR or SD (SD \geq 6 weeks) events, the study will continue recruiting up to 13 more patients in the second stage. When the total number of patients reaches the maximum sample size of 36, we reject the null hypothesis and conclude that the treatment is promising if the number of responses (CR or PR or SD(SD \geq 6 weeks)) are greater than 3; otherwise we conclude that the treatment is not promising.

No hypothesis for cohort 3 and cohort 4 of phase II since both cohorts are served as preliminary investigation or exploratory purpose.

6. Analysis Sets

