- **Cohort 2:** Patients with *BRAF/NRAS* (mutation sites as follows: *NRAS* G13V, *NRAS* Q61, *BRAF* V600, *BRAF* G469A, L485W, L597Q, T599dup) mutated non-small cell lung cancer;
- **Cohort 3:** Patients with *BRAF* V600 mutated Langerhans Cell Histiocytosis Syndrome (LCH)/Erdheim-Chester disease (ECD);
- **Cohort 4:** Patients with *RAS/RAF/MEK/ERK* mutated tumors that are not included in other cohorts.

The sample size in Cohort 1 and Cohort 2 is justified according to the Bayesian optimal phase 2 (BOP2) design [60]. Specifically, let n denote the interim sample size and N denote the maximum

sample size. Let p_{eff} denote the probability of efficacy (response rate) and define the null hypothesis $H_0: p_{eff} \leq 0.05$, representing that the treatment is ineffectual. We will stop enrolling patients and claim that the treatment is not promising if

$$- \quad Pr(p_{eff} > 0.05 | data) < \lambda \left(\frac{n}{N}\right)^\alpha,$$

where $\lambda=0.75$ and $\alpha=0.2$ are design parameters optimized to minimize the chance of incorrectly claiming that an efficacious treatment is not promising (i.e., type II error) under the alternative hypothesis $H_1: p_{eff} = 0.16$, while controlling the type I error rate at 0.1 (i.e., the chance of incorrectly claiming that an ineffectual treatment is promising is no more than 10%). Assuming a Beta (0.05,0.95) prior distribution for p_{eff} , the above decision rule corresponds to the following stopping boundaries and yields a statistical power of 0.8201 under H_1 :

[figure not shown]
Table 4-1 Optimized stopping boundaries for cohort 1 and cohort 2 in Phase II

# patients treated	Stop if # responses <=
23	1
36	3

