where $\lambda=0.75$ and $\alpha=0.2$ are design parameters optimized to minimize the chance of incorrectly claiming that an efficacious treatment is not promising (i.e., type II error) under the alternative hypothesis $H_1: p_{eff} = 0.16$, while controlling the type I error rate at 0.1 (i.e., the chance of incorrectly claiming that an inefficacious treatment is promising is no more than 10%). Assuming a Beta (0.05,0.95) prior distribution for p_{eff} , the above decision rule corresponds to the following stopping boundaries and yields a statistical power of 0.8201 under H_1 :

Table 10-1 Optimized stopping boundaries for cohort 1 and cohort 2 in Phase II

# patients treated	Stop if # responses <=
23	1
36	3

Based on [Table 10-1](#), we will perform an interim analysis for the first 23 patients. When at least 2 patients experience CR or PR or SD ($SD \geq 6$ month) events, the study will continue recruiting up to 13 more patients in the second stage. When the total number of patients reaches the maximum sample size of 36, we reject the null hypothesis and conclude that the treatment is promising if the number of responses is greater than 3; otherwise we conclude that the treatment is not promising.

We plan to recruit a maximum of 9 patients in Cohort 3. Since there are currently no sufficient data available (due to the rarity of the disease), we are unable to calculate the sample size provided for an acceptable statistical justification. However, at this stage, we think that data from 9 patients is considered to be adequate to allow a preliminary investigation of the study objectives for this cohort [60].

Cohort 4 will include a maximum of 27 patients. Patients included in this cohort will have different cancer types led by different genetic mutations. Thus, it is difficult to calculate sample size for this cohort based on very accurate efficacy goals (e.g. minimum ORR for the alternative hypothesis). Therefore, this cohort serves for an exploratory purpose and the number of patients has been based on the desire to obtain adequate data whilst exposing as few patients as possible to the study procedures.

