3.2 Sample Size

Phase I Dose Escalation Stage:

The planned maximum sample size in Phase I dose escalation stage (ATD + BOIN) is 58 including up to 40 subjects for ATD + QD dose escalation cohorts (Part A) and up to 18 subjects for the additional BID dose escalation cohorts (Part B). During the ATD, one-patient per cohort is required for dose escalation. Once the BOIN design starts, cohorts of 3 patients will be used for dose escalation and the maximum number of patients for each dose level should not exceed 15 patients and 12 patients for BOIN design Part A and Part B, respectively.

Phase I Dose Expansion Stage:

We plan to recruit 15 evaluable patients per expansion cohort in the phase I stage of the study. The enrolled patients with different cancers must have confirmation of specific MAPK pathway genetic alteration. The primary focus of the dose expansion is to further assess the safety and pharmacokinetics of HH2710. Preliminary efficacy will also be examined but serve only for an exploratory purpose.

Phase II Dose Extension Stage:

In Phase II, patients will be recruited into the following 4 cohorts at the RP2D level:

Cohort 1: Patients with BRAF/NRAS (mutation sites as follows: NRAS G13V, NRAS Q61, BRAF V600, BRAF G469A, L485W, L597Q, T599dup) mutated melanoma;

Cohort 2: Patients with BRAF/NRAS (mutation sites as follows: NRAS G13V, NRAS Q61, BRAF V600, BRAF G469A, L485W, L597Q, T599dup) mutated non-small cell lung cancer;

Cohort 3: Patients with BRAF V600 mutated Langerhans Cell Histiocytosis Syndrome (LCH)/ Erdheim-Chester disease (ECD);

Cohort 4: Patients with RAS/RAF/MEK/ERK mutated tumors that are not included in other cohorts.

Cohort 1-2 will utilize the Bayesian Optimal design for phase II trials (BOP2). The null hypothesis of the response rate is 0.05, and the alternative hypothesis is 0.16. The design controls the type I error rate at 0.1 and yields the power of 0.8201 under H1.

Table 3-1 Optimized stopping boundaries for cohort 1 and cohort 2 in Phase II

# patients treated	Stop if # responses \leq
23	1
36	3

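### SAP section 5 gives the Cohort 1 and 2 null response rate as 0.02, but the boundaries, error cap and power beside it belong to the 0.05 null in SAP 3.2 and the protocol

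*SAP*

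**What the plan says.** SAP section 5 (Hypotheses and/or Estimations): "In Cohort 1 and Cohort2, the null hypothesis of the response rate is 0.02, and the alternative hypothesis is 0.16". The next sentence reads "The design controls the type I error rate at 0.1 and yields the power of 0.8201 under H1". The section then gives the decision rule as counts. Recruitment continues beyond 23 patients if at least 2 have a qualifying event, and the null is rejected if more than 3 of 36 do.

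SAP 3.2 (Sample Size), for the same cohorts: "The null hypothesis of the response rate is 0.05, and the alternative hypothesis is 0.16". It gives the same error rate, power and boundaries (its Table 3-1: stop at 1 or fewer of 23; not promising at 3 or fewer of 36).

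Protocol 4.1 and 10.4 define the null as a response rate of at most 0.05 and the alternative as 0.16, with the same boundaries (Tables 4-1 and 10-1) and the same power. The error rate is described as "while controlling the type I error rate at 0.1", and 10.4 explains it as a ceiling: "the chance of incorrectly claiming that an inefficacious treatment is promising is no more than 10" per cent. The protocol also gives the generating rule: stop if Pr(p_eff > 0.05 | data) < λ(n/N)^α, with λ = 0.75, α = 0.2 and a Beta(0.05, 0.95) prior.

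SAP 8.12 lists the changes from the protocol, down to the number of decimals for percentages. It lists no change of null.

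**The concern.** The SAP contains two nulls for one test, and only one of them agrees with the protocol. Section 5 is where a reader looks for the hypothesis, so its value is the one likely to be copied into a report. Cohorts 1 and 2 carry the only Phase II hypotheses, since section 5 says that Cohorts 3 and 4 have none.

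If 0.02 stands, rejecting the null is a statement about exceeding 2%, which is a much weaker claim than the design was built to support. The error rate and boundaries printed in the same section would then describe a different null from the one named. With both values in the SAP, the hypothesis that is reported as rejected could also be chosen after the data are seen.

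**Working it through.** **Inputs.** Interim n = 23, maximum N = 36; continue at ≥ 2, promising at ≥ 4 (SAP section 5; SAP Table 3-1; protocol Tables 4-1 and 10-1). λ = 0.75, α = 0.2, prior Beta(0.05, 0.95) (protocol 4.1 and 10.4). Nulls 0.05 and 0.02; alternative 0.16. A response is taken as CR or PR throughout.

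**Step 1: which null generates the printed boundaries?** The posterior after x responses in n is Beta(a + x, 1 − a + n − x), where the prior is Beta(a, 1 − a). The cut-offs are 0.75 × (23/36)^0.2 = 0.6857 at the interim and 0.75 × (36/36)^0.2 = 0.75 at the end. The trial stops when Pr(p_eff > null | data) is below the cut-off.

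| Null, prior | 23 patients | 36 patients | Boundaries |
|---|---|---|---|
| 0.05, Beta(0.05, 0.95) | x=1: 0.3274; x=2: 0.6945 | x=3: 0.7431; x=4: 0.9017 | 1/23 and 3/36 |
| 0.02, Beta(0.02, 0.98), assumed | x=1: 0.6381; x=2: 0.9260 | x=1: 0.4929; x=2: 0.8426 | 1/23 and 1/36 |
| 0.02, Beta(0.05, 0.95) | x=1: 0.6524; x=2: 0.9299 | x=1: 0.5072; x=2: 0.8490 | 1/23 and 1/36 |

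The plan's own boundaries, 1/23 and 3/36, come back exactly at 0.05. With the same λ and α they do not come back at 0.02 under either prior.

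**Step 2: operating characteristics of the printed boundaries.** With X1 ~ Bin(23, p) and X2 ~ Bin(13, p),

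P(promising) = P(X1 = 2)·P(X2 ≥ 2) + P(X1 = 3)·P(X2 ≥ 1) + P(X1 ≥ 4).

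- p = 0.16: 0.1664 × 0.6396 + 0.2219 × 0.8963 + 0.5141 = 0.8195. The plan states 0.8201, a difference of 0.0006; rounding from simulation is a possible reason (assumption).
- p = 0.05: 0.2154 × 0.1354 + 0.0794 × 0.4867 + 0.0258 = 0.0936, within the cap of 0.10.
- p = 0.02: 0.0662 × 0.02695 + 0.00946 × 0.2310 + 0.00104 = 0.0050, which is 0.0050/0.10, or one-twentieth, of the cap.

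**Step 3: what depends on the null?** Once the counts are fixed, power at 0.16 does not involve the null, so 0.8201 is unaffected. The decision is also a function of the counts alone: 3 of 36 is not promising and 4 of 36 is promising, whichever null is printed. Only the hypothesis being rejected, and the type I error that belongs to it, change.

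**The case against.** The strongest reply is that nothing operative is wrong. The count rule in section 5 matches every other statement of it, and anyone who applies it reaches the intended decision. The power is right. The 0.1 is defined in the protocol as a ceiling, and 0.0050 lies below that ceiling, so even at 0.02 the statement about control is uninformative but not false. The correct null appears in SAP 3.2 and in two sections of the protocol. SAP section 7 adds that the programme has stopped and that many planned analyses may not be run. All of this stands, and it limits the severity.

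Three stronger readings are tempting, and the documents do not support them.

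- *The boundaries or error rates in section 5 are wrong, or the type I error is misstated twenty-fold.* They are correct for 0.05, and a ceiling is not overstated because the actual rate falls below it.
- *A programmer working from section 5 would reach a different decision.* Section 5 contains no posterior rule, λ, α or prior. Rebuilding the boundary means importing these from the protocol, where the same rule names 0.05. Such a rebuild at 0.02 would call 2 of 36 promising and raise the chance of a promising result at a true 5% from 0.0936 to 0.3206, but neither document specifies that design.
- *An exact p-value against 2% could contradict the table.* For 3 of 36 the fixed-sample one-sided value is 0.035, but no p-value is planned. SAP 8.7.1.2 plans ORR with a Clopper-Pearson interval.

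The objection does not remove the contradiction. The null in section 5 disagrees with SAP 3.2 and with the protocol, and no change is declared.

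**Conclusion.** The point holds as an inconsistency in one number. The 0.02 in SAP section 5 contradicts SAP 3.2 and protocol 4.1 and 10.4. The boundaries, the cap of 0.1 and the power of 0.8201 printed with it belong to 0.05. The undeclared difference looks like an uncorrected error and not a redesign.

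In size, the printed boundaries have a type I error of 0.0936 at 0.05 and 0.0050 at 0.02, with power of 0.8195 at 0.16 in both cases. The consequence is confined to the stated meaning of a rejection (above 2% instead of above 5%) and to how it is reported. Severity is minor to moderate.

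These probabilities assume that a response means CR or PR. The rule in section 5 also counts stable disease of at least 6 weeks. That is a separate matter, but it means that 0.0936 does not describe the rule as literally written there.

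**What to change.** In SAP section 5, replace 0.02 with 0.05. Leave the boundaries, the type I error cap and the power as they are. Do not add the exact type I error (0.094) to section 5 unless it is stated to apply to CR and PR responses only.

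The cost is one number in the SAP. No recalculation, change of sample size or protocol amendment is needed. If 0.02 was intended, it would have to be declared in SAP 8.12, SAP 3.2 would have to be reconciled with it, and the boundaries and error rates would need a new derivation; nothing in either document suggests this.

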6.1 Full Analysis Set (FAS)

The Full Analysis Set includes all patients who have received at least one dose of study medication. This set will be used for efficacy analysis.

6.2 Safety Analysis Set (SAS)

The Safety Analysis Set (SAS) includes all patients who receive at least one dose of study medication. This set will be used for safety analysis.

6.3 Pharmacokinetic Analysis Set (PKS)

The pharmacokinetic analysis set (PKS) consists of all patients who receive at least 1 dose of study drug and have sufficient, valid PK samples to estimate key parameters for at least 1 of the days of sampling.

6.4 Pharmacodynamics analysis set (PDS)

The pharmacodynamics analysis set (PDS) consists of all patients set who receive at least 1 dose of study drug and have sufficient, valid PD samples to estimate key parameters for at least 1 of the days of sampling.

6.5 Subgroup Analyses

Subgroup analyses will be performed to explore the consistency of the treatment effect when the sample sizes allows for meaningful interpretation. The following subgroup may be used to examine efficacy:

Sex (female vs. male)

Age (<65 vs. ≥ 65)

Race

Tumor type

Genetic mutation

7. Planned Analyses

The HH2710 program is stopped and this study is terminated ahead of time with a limited number of subjects treated than planned. As the result, many planned analyses will have insufficient data to render the planned analyses feasible, meaningful or interpretable. Therefore, many of the planned analyses described in this SAP may not be conducted, depending on data availability or maturity, and purpose of the analysis.

7.1 Interim Analysis and Early Stopping Guidelines

There are three planned interim analyses during the study. One is performed for the determination of RP2D when Phase I completes. The other two are conducted for futility evaluation for the first 23 patients in each of cohort 1 and cohort 2 when they have recruited and completed the assessments in Phase II. Additional or administrative interim analyses may be conducted as necessary by the sponsor for safety/efficacy monitoring while the study is ongoing.

A Safety Monitoring Committee (SMC) will be used to evaluate safety as well as preliminary efficacy during the study. In Phase I, safety data will be reviewed by the committee after a minimum of 3 patients have been enrolled into each dose level and received treatment. Once the dose escalation stage completes, the committee will review safety data as well as data from other sources (e.g. efficacy, PK/PD) to determine the RP2D for Phase II.

In Phase II, the efficacy review will be conducted for cohort 1 and cohort 2 by the committee when each cohort has recruited and completed the assessments for the first 23 patients. For safety, the committee will review the data when every 6 or 12 patients have recruited and received treatments in all cohorts. Following the data review, the committee will decide as to whether the cohort may continue, whether amendment(s) to the protocol should be implemented, or whether the study should be stopped.

Members of the committee will be internal and external to the sponsor, which can include employees of the Sponsor and study investigators.

7.2 Primary Analysis

The primary analyses in Phase I focuses on safety endpoints for HH2710 administered alone in patients with the advanced and/or refractory tumors. The RP2D will be determined based upon the observed DLTs and information from other sources (e.g. pharmacokinetics) as described in the protocol.

In Phase II, the primary analyses will investigate the preliminary efficacy of the ORR and other endpoints including DoR, DCR, TTR, TTP, PFS and 1-year OS rate, and by tumor

type and by genetic mutation if warranted. The RP2D might be adjusted based on the phase II data.

8. Statistical Methods of Analysis

8.1 General Principles

TFLs will be displayed by treatment groups, which are the dose levels for phase I study and cohort levels for phase II study. If necessary, the same dose level may be combined and analyzed across phase I and II studies.

Continuous variables will be summarized using the following descriptive summary statistics: the number of subjects (n), mean, standard deviation (SD), median, minimum value (min), and maximum value (max). The number of subjects (n) will represent the number with non-missing data on the continuous variable under consideration. The precision of the measurement for each continuous variable will be used to determine the number of decimal places to present in tables, figures, and derived listings. Unless otherwise specified, min and max values will be reported with the same decimal as the units of measure; the mean, median will be reported to 1 greater decimal place, the SD will be reported to 2 greater decimal place, all of them will not be greater than 4 decimal place. Any values that require transformation to standard units (metric or International System [SI]) will be converted with the appropriate corresponding precision.

Categorical variables will be summarized using counts and percentages (95% confidence interval of percentage if necessary). Percentages will be presented to 1 decimal place unless otherwise specified.

Treatment group indicates the dose level of HH2710 (such as 25 mg BID) and total (if more than one dose level) for phase I and cohort in Phase II.

Baseline value, unless otherwise specified, will be defined as the last non-missing measurement (scheduled or unscheduled) collected prior to the initial administration of study drug. For example, if an assessment was performed at screening and Day 1 prior to initial dosing of study drug, then Baseline is the Day 1 measurement if the Day 1 value is not missing; if the Day 1 value is missing, then the screening value is Baseline, and so forth.

Change (absolute change) from baseline will be calculated as post-baseline value - baseline value.

Unscheduled visits: Subject data for safety or efficacy assessments (such as unscheduled labs) will be incorporated into the cycle windows appropriate to the scheduled visits. For summary by visit tables and figures, only scheduled visits will be included in the analysis.

Incomplete/missing data: Unless otherwise specified, for efficacy and safety analysis, no imputation will be used. If a partial dates need to be imputed for computational purposes, conservative conventions will be used as far as possible.

All statistical analyses will be performed using SAS 9.4 (SAS Institute, Cary, North Carolina, USA).

8.2 Major Protocol Deviations

Major Protocol Deviations (MPDs) categories are defined by the study team before the first subject's visit and updated during the MPD reviews throughout the study prior to database lock. These definitions of MPD categories, sub-category codes and descriptions will be used during the course of the study.

For phase I and phase II, a summary of the number and percentage of subjects with a major protocol deviation by type of deviation will be provided using the full analysis set. Individual subject listings of protocol deviations will be provided.

8.3 Demographic and Baseline Characteristics

For phase I and phase II, demographic (ie, age, age group [<65 , ≥ 65], sex and race) and baseline disease characteristics will be summarized using descriptive statistics for the full analysis set. Though different names, these two sets have the same definition and subjects.

The baseline characteristics to be summarized include:

- Weight (kg)
- Height (cm)
- Body mass Index (kg/m **2)
- ECOG performance status
- Tumor Histology and pathology type
- Tumor Stage
- Genetic mutation type
- Number of metastases at baseline
- Location of metastases at baseline
- Subject received any prior systemic anti-tumor therapy: Number of prior lines or regimens of therapy, Best overall response
- Received radiotherapy for Tumor
- Received surgery for Tumor

